#### **3.3 Exclusion criteria**

Exclusion criteria:

- 1) Member of a protected population (pregnant, prisoner)
- 2) Known history of kidney stones within the past 1 year (not including incidentally noted stones noted on imaging studies)
- 3) End stage renal disease requiring dialysis (hemodialysis or peritoneal dialysis)
- 4) Known history of G6PD deficiency
- 5) Known history of Hemochromatosis
- 6) Comfort Measures Only status
- 7) Anticipated death within 24-hours despite maximal therapy (as determined by the enrolling physician)
- 8) Receiving supplemental vitamin B1 in a dose greater than that contained in a multivitamin (<2mg)
- 9) Clinical indication for steroids (e.g. chronic use) as determined by the clinical team providing this drug
- 10) Clinical indication for ascorbic acid supplementation in any form
- 11) Clinical indication for vitamin B1 as determined by the clinical team providing this drug
- 12) Known allergy to vitamin C, hydrocortisone, or vitamin B1

Justification of Inclusion and Exclusion Criteria: The inclusion criteria were chosen to isolate a septic participant population with high risk of organ injury and death. The exclusion criteria were chosen to minimize the risk of potential harm and to ensure that participants enrolled do not already have chronic end-stage renal failure with a high likelihood of early need for renal replacement therapy. By evaluating this high-risk population (i.e., most likely to die), we will target those most likely to benefit and therefore increase the probability of showing efficacy.

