##### 5.1.2 Key Secondary Outcomes

Incidence of Acute Renal Failure – Renal failure will be defined as the development of Kidney Disease Improving Global Outcomes [KDIGO] Stage 3 acute kidney injury during the index ICU stay after study enrollment.

KDIGO Stage	Serum creatinine criteria	Urine output criteria
1	Increase in serum creatinine of more than or equal to 0.3 mg/dl ( $\geq$ 26.4 $\mu$ mol/l) or increase to more than or equal to 150% to 200% (1.5- to 2-fold) from baseline	Less than 0.5 ml/kg per hour for more than 6 hours
2	Increase in serum creatinine to more than 200% to 300% (> 2- to 3-fold) from baseline	Less than 0.5 ml/kg per hour for more than 12 hours
3	Increase in serum creatinine to more than 300% (> 3-fold) from baseline (or serum creatinine of more than or equal to 4.0 mg/dl [<math>\geq</math> 354 <math>\mu</math>mol/l]) with an acute increase of at least 0.5 mg/dl [44 <math>\mu</math>mol/l])	Less than 0.3 ml/kg per hour for 24 hours or anuria for 12 hours OR New renal replacement therapy (RRT)

**30-Day Mortality** – Mortality at 30-days. This will be assessed by review of the medical records if the participant remains in the hospital or if the participant expired while in the hospital. If the participant was discharged, 30-day mortality will be assessed by contacting the participant by phone or by searching the National Center for Health Statistics (NCHS) National Death Index (NDI) consistent with a recent multicenter phase III trial in sepsis. Phone calls will be made by the research team at each site.

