## 6. SAMPLE SIZE CALCULATION AND STATISTICAL ANALYSIS PLAN

### 6.1 Sample size calculation

The study has been powered to have at least 80% power for the primary outcome and all key secondary outcomes as follows:

**SOFA Score:** Based on preliminary data, we conservatively anticipate a decrease in SOFA score of 6 (standard deviation [SD]: 4) in the treatment group and 4 (SD: 2) in the placebo group. With these estimates, enrollment of **200 participants (100/arm)** at an alpha of 0.05 and using a t-test with unequal variance, the trial will provide > 99% power to detect a statistical significant difference between groups.

**Kidney Injury:** Based on preliminary data from our study of vitamin B1 in septic shock, we anticipate that 30% of participants in the treatment group and 55% in the placebo group will have renal failure which will result in a 94% power for this outcome. This calculation and following calculation were performed using the Fisher's exact test.

**Mortality:** Based on preliminary data, we anticipate that the control group will have a mortality of 40%. We estimate a treatment effect of 50% (risk ratio: 0.50) resulting in a mortality of 20% in the treatment group. With these estimates, 182 participants will lead to 80% power. To further increase

the trial's power and due to potential loss-to-follow-up, we will aim to enroll 200 participants. These estimates are conservative compared to the Marik et al. study which found a treatment effect corresponding to a risk ratio of 0.21 which persisted in adjusted analysis.

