## 6.2 Statistical analysis plan

### 6.2.1 General considerations

The statistical analyses and reporting will adhere to the CONSORT guidelines. All tests will be two-sided, a p-value  $< 0.05$  will be considered significant, and all confidence intervals will have 95% coverage. All analyses will be conducted on a modified intention-to-treat basis only including participants receiving at least the first dose of the study medications. In a double-blind trial, this approach is unbiased while increasing precision. The two groups will be compared in relation to baseline characteristics using descriptive statistics.

The persons conducting the statistical analysis will be blinded to the randomized allocation. Groups will be designated as "A" and "B" until all pre-specified analyses are performed and shared with all authors and the Data Safety Monitoring Board.

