### 6.2.2 SOFA score and renal failure

The change in SOFA score will be calculated and compared between groups using the Wilcoxon Rank Sum test (if the change is not normally distributed) or by a t-test if the change is approximately normally distributed. Fisher's exact tests will be used to compare the incidence of renal failure during the index ICU stay.

If a participant expires prior to the 72-hour time point, SOFA scores will be imputed based on a pre-defined plan as follows. If a participant expires before 24-hours has elapsed, a 20% increase from baseline will be imputed. If a participant expires between 24-hours and 48-hours, a 15% increase from the 24-hour time point will be imputed. If a participant dies between 48-hours and 72-hours, a 20% increase from the 24-hour time point will be imputed. Sensitivity analyses will be performed using various other imputation techniques. Specifically, we will perform 1) a sensitivity analysis in which the worst possible SOFA score (score of 24) is imputed for those participants who expire, 2) a sensitivity analysis in which the last SOFA score for participants who expire will be carried forward, and 3) a sensitivity analysis in which only those patients who survive to 72-hours are included. These sensitivity analyses were chosen to model 'worst-possible' and 'best-possible' scenarios. For the secondary outcome of renal failure, participants who expire during their ICU stay will be assessed to have developed renal failure if they demonstrated any degree of unresolved KDIGO acute kidney injury prior to death. If there was no evidence of acute kidney injury prior to death or if kidney injury had fully resolved, these participants will be assessed as not having developed renal failure.

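### Renal failure: participants already at KDIGO Stage 3 or on acute RRT at T1 are analysed with no rule for classifying them; an at-risk analysis set would be a cheap improvement

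*Protocol*

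**What the plan says.** Protocol 5.1.2 defines this key secondary outcome as the development of KDIGO Stage 3 "acute kidney injury during the index ICU stay after study enrollment". The RRT criterion in its staging table is limited to new RRT. The table measures creatinine rises from a baseline that it does not define.

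The only renal-function exclusion in Protocol 3.3 is "End stage renal disease requiring dialysis (hemodialysis or peritoneal dialysis". Acute Stage 3 injury or acute RRT at entry is no bar. Section 4.3 allows consent up to 24 hours after vasopressors start.

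Section 6.2.1 sets the population: "All analyses will be conducted on a modified intention-to-treat basis only including participants receiving at least the first dose of the study medications". Section 6.2.2 adds that Fisher's "exact tests will be used to compare the incidence of renal failure during the index ICU stay", without adjustment for renal status at entry. It has one special rule: a participant who dies in the ICU with any unresolved acute kidney injury (AKI) counts as having renal failure.

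Section 6.1 expects "30% of participants in the treatment group and 55% in the placebo group will have renal failure which will result in a 94% power". The source is given as "Based on preliminary data from our study of vitamin B1 in septic shock", with no statement of whether the denominator was everyone or only those at risk. The current protocol text reproduced in the SAP says the same in the same-numbered sections.

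**The concern.** An outcome defined as developing a state after enrolment normally takes its denominator from people not yet in that state. Here everyone is on vasopressors, possibly for up to a day. Protocol 5.2 puts renal failure at over 50% in septic shock; that is overall occurrence, not prevalence at entry, but it makes some prevalent cases plausible.

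The plan does not remove, classify or adjust for them, so two sites could code the same patient differently. If treatment does not influence the coding, these participants carry no information about prevention and dilute the absolute contrast. Section 5.2 says this outcome could change practice independently of the others, so its numerator and denominator should be unambiguous.

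**Working it through.** **Inputs.** From Protocol 6.1, 6.2.1 and the overview: 30% vs 55%, 100 per arm, two-sided 0.05, Fisher's exact test ("This calculation and following calculation were performed using the Fisher's exact test"). The prevalence f of Stage 3 or acute RRT at T1 is not in the documents. It is assumed, equal in both arms, at 5-30% (5-20% in step 4).

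**1. The plan's own figure.** Power is the sum over all (x1, x2) of Bin(x1; 100, 0.30) × Bin(x2; 100, 0.55) for tables with Fisher p < 0.05. Result: 93.9%, agreeing with 94%. As a check on the code, 40% vs 20% mortality with 91 per arm gives 80.8%, in line with the stated 80% at 182 participants.

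**2. Effect measures, if 30%/55% are at-risk rates and coding does not depend on treatment.**
- Coded as events: p = f + (1−f)p0. At f = 20%: 0.20 + 0.8×0.30 = 0.44 and 0.20 + 0.8×0.55 = 0.64. Risk ratio 0.44/0.64 = 0.69.
- Coded as non-events: p = (1−f)p0. At f = 20%: 0.24 and 0.44. Risk ratio 0.24/0.44 = 0.55, the same as 0.30/0.55.
- In both, the risk difference is (1−f)×25 points, or 20 points at f = 20%.

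**3. Power under the same reading.** The at-risk set has 100(1−f) per arm at 30% vs 55%.

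| f | All dosed, events | All dosed, non-events | At-risk set |
|---|---|---|---|
| 5% | 91.1% | 91.5% | 92.0% |
| 10% | 87.7% | 88.5% | 90.8% |
| 20% | 78.8% | 81.5% | 86.2% |
| 30% | 67.2% | 73.2% | 81.4% |

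The 80% floor in 6.1 is lost in the all-dosed analysis from about f = 19% (events) or 22% (non-events). The at-risk set loses it at 68 per arm or fewer.

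**4. Power if 30%/55% are whole-cohort rates.** The all-dosed analysis keeps 93.9%. The implied at-risk rates are (p−f)/(1−f) if prevalent cases were events, or p/(1−f) if they were non-events.

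| f | At-risk set, prevalent were events | At-risk set, prevalent were non-events |
|---|---|---|
| 5% | 95.0% (26.3% vs 52.6%) | 94.3% (31.6% vs 57.9%) |
| 10% | 96.8% (22.2% vs 50.0%) | 94.9% (33.3% vs 61.1%) |
| 20% | 99.3% (12.5% vs 43.8%) | 97.1% (37.5% vs 68.8%) |

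**5. Prevalent cases counted only through the ICU-death rule.** With at-risk rates again, p = (1−f)p0 + f×d, where d is the assumed proportion of prevalent cases dying in the ICU with unresolved AKI.
- d = 40% in both arms: 88.0%, 79.0% and 67.0% power at f = 10%, 20% and 30%.
- d = 40% placebo and 20% treatment (borrowing the 30-day mortality rates in 6.1): at f = 20%, 0.8×0.30 + 0.2×0.20 = 0.28 vs 0.8×0.55 + 0.2×0.40 = 0.52. Power is 93.0%, 92.1% and 91.1% at f = 10%, 20% and 30%.

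**The case against.** A reader might infer that these participants cannot have the outcome and that their status is settled before treatment. The documents do not support that. Section 6.2.2 counts them as events if they die in the ICU with unresolved AKI, and a participant at Stage 3 by creatinine or urine output can still start new RRT. Step 5 shows the consequence: if treatment halves such deaths, the all-dosed analysis keeps 91-93% and beats the at-risk set. This objection stands. But that contrast would come from mortality, which is already a separate key secondary outcome, not from prevention of renal failure.

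A reader might also infer that the 94% is wrong. It is correct on its stated inputs. A loss follows only if 30%/55% are at-risk rates and prevalence is material, and the documents settle neither. Nor does the risk ratio necessarily move toward 1; under non-event coding it does not change.

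Three further points on the other side:
- The all-dosed comparison is randomised and unbiased. That is true, but so is a set defined by status before the first dose, which treatment cannot affect.
- The Sample Size Adjustment text in 6.1 allows a larger trial if the renal event rate is low. It gives numeric power targets only for SOFA and mortality.
- Section 8.1.2 says that known renal failure is excluded. The criteria in 3.3 carry this out only for end-stage disease on dialysis; the two passages should be reconciled.

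Finally, an at-risk set cannot be built from the T1 blood draw alone. Staging needs a reference creatinine, which is undefined, and up to 24 hours of prior urine output. This stands and is part of the fix.

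**Conclusion.** The point holds as a cheap improvement, not as an error in the power statement. The firm part rests on the text alone: the outcome is incident Stage 3 or new RRT, prevalent cases may enter, and nothing says how to count them.

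The size is conditional. With at-risk rates and coding unrelated to treatment, keeping them in costs about 2-3 points of power against an at-risk set at an assumed 10% prevalence, 5-7 points at 20% and 8-14 points at 30%. With whole-cohort rates the plan loses nothing against its 93.9%, and the at-risk set still does slightly to moderately better (about 94-99% at 5-20% prevalence). The at-risk set therefore has more power on either reading of the rates, unless treatment changes how prevalent cases are coded, chiefly through ICU deaths.

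**What to change.** In 6.2.2:
- Define the reference creatinine used for KDIGO staging, and which pre-T1 urine output and RRT records establish status at T1.
- Make the main analysis set for renal failure the dosed participants without KDIGO Stage 3 injury or RRT at T1.
- Report the all-dosed comparison as a sensitivity analysis, with a stated coding for prevalent cases (event, non-event, or event only through the ICU-death rule).

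In 6.1, say whether 30%/55%, and so the 94%, refer to all enrolled or to those at risk. If at risk, add an assumed prevalence and recompute the power.

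The cost is SAP wording, a smaller denominator for this one outcome, and the need for prior creatinine and urine output. Where those are missing at T1, the SAP needs a default classification fixed before unblinding.

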## 5.2 Rationale for Outcomes

**Change in SOFA score:** Organ failure is highly associated with mortality and improvement in organ function is a key goal for critical care physicians. In the study by Marik et al., participants who received the 3-drug regimen had substantial improvements in the trajectory of organ failure over the first 72-hours of their ICU stay. If the combination of vitamin C, hydrocortisone, and vitamin B1 can improve organ function in the first 72-hours following ICU admission, we believe that clinicians will likely quickly adopt this safe and inexpensive therapy. Importantly, this outcome can be measured early in the hospital stay and is therefore less likely to be affected by other potential elements of hospital care that can affect more distal outcomes (e.g., mortality).

**Kidney Injury:** Renal failure has been estimated to occur in 23% of participants with sepsis and over 50% of participants with septic shock. In studies of participants with septic shock, there is a step-wise increase in mortality with worsening acute kidney injury (AKI). In addition, many participants who experience renal injury during septic shock do not recover renal function prior to hospital discharge and may require long term dialysis. As both data from the study by Marik et. al. and a separate study of vitamin B1 in septic shock have shown substantial improvements in renal outcomes, kidney failure is a natural secondary outcome and one that could change practice independently from other factors – in other words, many clinicians would likely provide this therapy if they knew that kidney function could be protected, since this organ is vital to long-term health.

**Mortality:** Finally, we will measure 30-day mortality. We anticipate that the combination of vitamin C, hydrocortisone, and vitamin B1 will reduce mortality in this high-risk population.

## 5.3 Additional Secondary Outcomes

### 5.3.1 Additional secondary outcomes

Additional secondary outcomes will include length of ICU stay, length of hospital stay, ventilator-free days over the first 7-days after enrollment, shock-free days over the first 7-days after enrollment,

and the incidence of delirium on day #3 of the ICU stay (as assessed using the Confusion Assessment Method [CAM-ICU] system). Sites at which the CAM-ICU is performed daily as part of standard-of-care should assess whether delirium occurs on any day during the initial ICU stay. See Appendix #2.

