#### **4. TRIAL PROCEDURES**

##### **4.1 Participant Identification**

Screening will be performed in the emergency department and intensive care units (ICUs) with the assistance of electronic screening mechanisms. Detailed screening logs, with reason(s) for exclusion will be kept at each site and reported in the final publication.

We anticipate that all patients, as part of standard-of-care for the septic patient, will have a urine or serum HCG test performed (if a female of child-bearing age). If this test is not sent as part of standard-of-care, it should be sent prior to consent.

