##### **4.3 Randomization**

After consent is obtained, the research team will notify the local research pharmacy. The research pharmacy will be in possession of the randomization list and will determine which arm (intervention vs. placebo) the participant will be enrolled in.

Patients should be randomized, consented, and enrolled in the study as soon as possible after meeting inclusion criteria. Patients should not be *consented* if it has been >24hours since the patient met inclusion criteria (i.e. start of vasopressors). At the time of randomization and study drug administration, the patient should still be receiving a vasopressor. The patient should not be given study drug if the vasopressor has been stopped (e.g. patient met inclusion criteria overnight but could not be consented for logistical reasons and then improves to the point of no longer requiring a vasopressor). In this scenario, the patient will be entered into the database as consented but not enrolled.

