### 6.2.4 Additional Secondary Analyses

Both ICU and hospital length of stay will be compared using Wilcoxon Rank Sum tests. Ventilator and shock free days over the first 7-days after enrollment will likewise be compared using the Wilcoxon Rank Sum given that the data will likely be not normally distributed. In these latter two analyses, patients who expire prior to 7-days will be assessed to have 0 ventilator or shock free days if they had died while on a ventilator or vasopressor respectively. The incidence of delirium will be compared using the Fisher's exact test. For the quality-of-life outcome (i.e. 90-day SF-36), the primary analysis will only include patients with available data. As a secondary analysis, multiple imputation will be used to estimate SF-36 scores in all patients not known to be dead at 90 -days.

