### 718 *6.2.4 Additional Secondary Analyses*

719 Both ICU and hospital length of stay will be compared using Wilcoxon Rank Sum tests. Ventilator  
720 and shock free days over the first 7-days after enrollment will likewise be compared using the

721 Wilcoxon Rank Sum given that the data will likely be not normally distributed. In these latter two  
722 analyses, patients who expire prior to 7-days will be assessed to have 0 ventilator or shock free  
723 days if they had died while on a ventilator or vasopressor respectively. The incidence of delirium will  
724 be compared using the Fisher's exact test. For the quality-of-life outcome (i.e. 90-day SF-36), the  
725 primary analysis will only include patients with available data. As a secondary analysis, multiple  
726 imputation will be used to estimate SF-36 scores in all patients not known to be dead at 90 -days.  
727

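### Delirium is timed from ICU admission instead of enrolment, so pre-treatment values can be counted, and the analysis section does not say which of two assessment windows is tested

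*Protocol*

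**What the plan says.** Protocol section 5.3.1 gives the outcome as "the incidence of delirium on day #3 of the ICU stay", assessed by CAM-ICU. The next sentence says that sites performing CAM-ICU daily in routine care "should assess whether delirium occurs on any day during the initial ICU stay". The text does not say whether the any-day assessment replaces the day-3 value at those sites or is collected as well, and it does not say how ICU days are numbered.

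Section 6.2.4 gives one line of analysis: "The incidence of delirium will be compared using the Fisher's exact test". It names no window and gives no rule for the two kinds of site. The SAP repeats both sections without change.

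The neighbouring outcomes are anchored differently. Section 5.3.1 itself specifies "shock-free days over the first 7-days after enrollment" and counts ventilator-free days the same way. Section 5.1.2 limits renal failure to the part of the index ICU stay that follows enrolment.

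On timing of entry, section 4.3 bars consent "if it has been >24hours since the patient met inclusion criteria (i.e. start of vasopressors"). Section 4.1 says "Screening will be performed in the emergency department and intensive care units (ICUs"), so patients already in an ICU can be enrolled. Nothing in sections 3.2 or 3.3 limits the time already spent there.

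**The concern.** An outcome measured before the first dose cannot respond to treatment. The entry clock starts at vasopressors and the delirium clock starts at ICU admission, so the two can separate. A patient whose septic shock begins late in an ICU stay is eligible, and that patient's ICU day 3 may already be over. The any-day window has the same weakness in another form: a patient who was delirious before enrolment counts as a case whatever the treatment does afterwards.

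Both effects shrink a true difference, in either direction. The direction of harm has some relevance because section 8.1.2 names delirium among the hypothetical risks of hydrocortisone, and delirium is absent from the specific adverse-event table in 5.4.2. The same paragraph of 8.1.2 adds that these risks have not been seen in sepsis trials of corticosteroids, so this is a reason for a clean definition and not evidence of a safety problem.

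The second gap is that 6.2.4 leaves the tested variable open. A one-day prevalence and a whole-stay incidence are different quantities, and a reader of the result would need to know which one was compared.

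**Working it through.** **Tool check.** The plan gives no rate, effect or power for delirium, so there is no delirium figure to reproduce. The same test is used for renal failure in section 6.1. Exact two-sided Fisher power by full enumeration, 55% vs 30%, 100 per arm, alpha 0.05, is 93.9%; the plan states 94%.

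**Timing.** Assume that ICU day 3 means hours 48 to 72 of the stay, and let enrolment (taken as the first dose) fall at ICU hour e. Day 3 then lies between (48 − e) and (72 − e) hours after enrolment.

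| e (hours) | ICU day 3 relative to enrolment |
|---|---|
| 0 | 48 to 72 h after |
| 24 | 24 to 48 h after |
| between 48 and 72 | partly before, partly after |
| 72 or more | wholly before |

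The last row is reachable. With up to 24 hours allowed from vasopressor start to consent, it needs vasopressors to start at about ICU hour 48 or later (72 − 24 = 48), and nothing in the eligibility criteria prevents that.

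**Dilution by pre-enrolment values.** Assumptions, none from the documents: true delirium 45% vs 25%, and a share s of patients in each arm whose recorded value precedes treatment and so has a 45% rate in both arms. The sample size of 100 per arm and two-sided alpha of 0.05 are the plan's.

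Observed treated rate = (1 − s) × 25% + s × 45%. Difference = (1 − s) × 20 points. For example, at s = 10%: 0.9 × 25 + 0.1 × 45 = 27%, a difference of 18 points.

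| s | Treated rate | Difference (points) | Fisher power |
|---|---|---|---|
| 0% | 25.0% | 20.0 | 80.9% |
| 1% | 25.2% | 19.8 | 80.0% |
| 2% | 25.4% | 19.6 | 79.1% |
| 5% | 26.0% | 19.0 | 76.2% |
| 10% | 27.0% | 18.0 | 70.9% |
| 20% | 29.0% | 16.0 | 59.5% |

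**How different the two windows are.** With an assumed daily delirium probability q and independent days, any-day incidence over five ICU days is 1 − (1 − q)^5. At q = 20% this is 1 − 0.8^5 = 67%; at q = 40% it is 1 − 0.6^5 = 92%.

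**What combining them would do.** Assume day-3 rates of 30% vs 15%, which alone give power of 66.9% at 100 per arm. Let half the patients contribute any-day values instead.

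- Any-day 60% vs 50%: pooled (30 + 60)/2 = 45.0% vs (15 + 50)/2 = 32.5%; risk ratio 0.72 in place of 0.50; power 38.8%.
- Any-day 60% vs 30%: pooled 45.0% vs (15 + 30)/2 = 22.5%; risk ratio stays 0.50; power 90.2%.

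The direction therefore depends entirely on the assumed any-day effect.

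**The case against.** A reader might infer that the plan pools day-3 and any-day values in one test. The documents do not say so. Section 5.3.1 names day 3 as the outcome, and the any-day sentence can be read as extra data collection at sites that would also hold a day-3 value. On that reading, a common day-3 outcome exists for all sites. This stands: pooling is possible but not stated, and what can be criticised is that 6.2.4 does not name the variable.

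A reader might also infer that mixing the windows must weaken the comparison or make it meaningless. The two pooled examples show that power can fall or rise. Randomisation is stratified by site (section 2.2), so within a site both arms share the same window, and the test of no difference remains valid for whichever window is fixed.

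Finally, late enrolment may be rare. Screening includes the emergency department, section 4.3 asks for prompt enrolment and caps consent at 24 hours from vasopressor start, and section 5.2 presents the first 72 hours after ICU admission as the period of interest. A share of 1 to 2% would cost less than two points of power in the example. This also stands as to size. It does not remove the rule's defect, because nothing excludes shock that begins late in an ICU stay, and the any-day window can include pre-enrolment days even for patients enrolled on ICU day 2.

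**Conclusion.** The concern holds as a flaw of anchoring and specification. As written, both delirium windows can count pre-treatment values, and such values move any treatment difference toward zero. The section on analysis does not identify the tested window.

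The size is unknown, because the documents give neither delirium rates nor the share of patients enrolled after ICU day 3. Under the assumed 45% vs 25%, the loss runs from about 1 point of power at a 1% share to about 21 points at 20% (80.9 − 59.5 = 21.4). Those figures cover pre-enrolment dilution only; they say nothing about combining windows, whose effect could go either way. Type I error is not affected. This is a minor point on an additional secondary outcome for which the plan claims no power, and the primary and key secondary outcomes are untouched.

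**What to change.** In section 5.3.1 of both documents, define the outcome at every site as CAM-ICU status on study day 3, 72 hours after the first study drug, at the T3 time-point already scheduled in section 4.5. Name that variable in 6.2.4 as the one compared by Fisher's exact test. Report any-day delirium from daily-CAM sites as a separate supplementary outcome, limited to days after the first dose.

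State in 6.2.4 how patients are counted who by then have died, have left the ICU or cannot be assessed. Without that rule, moving to a fixed 72-hour assessment would replace one ambiguity with another.

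The cost is wording in the protocol, SAP and CRF. Daily-CAM sites should already hold the value for patients still in the ICU. Other sites re-time one assessment that they already plan. The small downside is that some patients will have no ICU assessment at 72 hours.
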